Sections 3.4.4.1., 3.4.5.1., 3.4.6.1., and 3.4.7.1. and 3.4.10.	For clarity, text has been reworded to reflect total amount of blood to be taken by study duration and to correct the blood volume to be collected for some assessments. In addition, a statement has been added to allow remaining blood samples to be used for further exploratory work in the context of the development of caplacizumab.
Section 3.4.8.5.	For clarity, the body systems to be examined during physical examination have been added.
Section 3.5.1.3.	The word "(specify)" has been deleted with regard to causal relationship of any AE to PE or use of corticosteroids to avoid confusion on what is to be specified (AE, PE parameter or corticosteroid).
Section 3.5.6.1.	More details concerning pregnancy reporting have been added.
Sections 3.6.5. and 3.6.6.	Wording has been updated to better reflect the planned analysis approach.
Appendix 9.1.	The appendix has been updated to reflect the latest version of the GCS.

Version 3.0 (dated July 20, 2016) compared to Version 2.0 (dated April 8, 2016). This amendment is considered substantial due to a change in planned sample size.	
Version n° and date were adapted throughout the document (including headers and footers). The Table of Contents was updated and the Section "Changes Compared to Previous Version(s)" was completed.	
Original section	Change/Rationale
Synopsis, Sections 3.1.1. and 3.2.	The number of subjects planned to be included in the study has been increased from 92 to 132 to account for a change in the assumed treatment difference for the primary endpoint in the sample size calculation (to bring it in line with the results of the Phase II study), to account for drop-outs, and to increase the statistical power of the key secondary endpoint analyses.
Synopsis and Section 3.6.4.2.	Clarification to ensure consistency.
Schedule of Assessments and Section 3.4.9.1.	Assessment of usability of the IMP kit has been removed from the Schedule of Assessments as the reporting only occurs in case of issues with preparation and/or administration of the study drug by the subject (or the caregiver, if applicable).

PROTOCOL SYNOPSIS

Protocol title:

A Phase III double-blind, randomized, parallel group, multicenter placebo-controlled trial to study the efficacy and safety of caplacizumab in patients with acquired thrombotic thrombocytopenic purpura.

Protocol short title:

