The hypothesis of interest in this study is to test the superiority of caplacizumab compared to placebo with respect to the time to platelet count response (initial platelet count $\geq 150 \times 10^9/L$ with subsequent stop of daily PE within 5 days). The required sample size is calculated to obtain a power of at least 80% to detect a significant reduction in time to platelet count response using a two-sided Log-rank test, at a significance level of 5%. The accrual period is taken to be 2.5 years and the time-to-event period is set at 45 days. An estimated reduction of time to platelet count response for subjects in the caplacizumab arm of 40% is assumed. With a median time to response in the placebo arm assumed to be 7 days, this would correspond with a median time to response in the caplacizumab arm of 4.2 days. In addition, an expected drop-out rate of 10% in the first 10 days after first administration of study drug is taken into account in the calculations. Based on these assumptions a total sample size of 132 subjects (121 events) will provide a power of 80%. A total sample size of 132 subjects will also provide approximately 83% power to detect a 20% reduction in the first key secondary endpoint, using a two-sided chi-squared test with a large sample approximation and a 5% significance level. This assumes an incidence of 30% and 10% in the placebo and caplacizumab arms, respectively.

Randomization:

Subjects will be randomized to one of the 2 arms in a 1:1 ratio. Randomization will be stratified by severity of neurological involvement (GCS ≤ 12 vs. GCS=13-15). Stratification is foreseen to ensure balanced treatment arms for the key secondary endpoints related to

neurological involvement and not for the primary endpoint for which the stratification parameter is not known to be relevant.

Analysis of primary endpoint:

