The efficacy and safety of caplacizumab in the treatment of acquired TTP have been evaluated in trial ALX-0681-2.1/10 comparing it to placebo when added to daily PE and in the 30-day post-daily PE period. The trial was terminated early due to recruitment challenges, with a total of 75 subjects enrolled and included in the intent-to-treat (ITT) analysis, but nonetheless demonstrated a statistically significant treatment effect as evidenced by the primary endpoint "time to confirmed platelet count normalization", with a hazard rate ratio (95% CI) for the caplacizumab versus placebo groups of 2.2 (1.3, 3.8), p-value for the stratified log-rank test of p=0.0048. This corresponded to a reduction in median time to confirmed platelet count normalization from 4.8 (3.6, 5.9) days in the placebo treatment group to 3.0 (2.8, 3.9) days in the caplacizumab treatment group.

The secondary endpoints illustrate the potential protective effect of caplacizumab treatment in the acute phase of TTP.

- Complete remission following initial daily PE was observed in a much higher number and proportion of subjects who received caplacizumab compared with the placebo group (29 [80.6%] subjects versus 18 [46.2%] subjects, respectively).
- A lower proportion of subjects with an exacerbation during treatment of 8% (n = 3) for caplacizumab compared to 28% (n = 11) for placebo.
- When the 1-month FU is also considered, a similar number and proportion of subjects had an exacerbation of TTP and/or a relapse of TTP (10 [27.8%] subjects in the caplacizumab treatment group and 11 [28.2%] subjects in the placebo treatment group). This suggests that in a number of subjects, the underlying auto-immune activity had not sufficiently resolved. Immunosuppressive treatment was not standardized and the shorter duration of PE in the caplacizumab arm may also have impacted the timing of the resolution of the underlying auto-immune disorder.

- The mean number of PE days during the initial daily PE period was lower in the caplacizumab group compared with the placebo group (5.9 versus 7.9, respectively), as was the mean total volume of PE administered (19923 mL versus 28307 mL, respectively).

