3.2 Determination of sample size

The primary hypothesis of interest in this study is to test the superiority of caplacizumab compared to placebo with respect to the time to platelet count response (initial platelet count $\geq 150 \times 10^9/L$ with subsequent stop of daily PE within 5 days). The required sample size is

calculated to obtain a power of at least 80% to detect a significant reduction in time to platelet count response using a two-sided Log-rank test, at a significance level of 5%. The accrual period is taken to be 2.5 years and the time-to-event period is set at 45 days. An estimated reduction of time to platelet count response for subjects in the caplacizumab arm of 40% is assumed. With a median time to response in the placebo arm assumed to be 7 days, this would correspond with a median time to response in the caplacizumab arm of 4.2 days. In addition, an expected drop-out rate of 10% in the first 10 days after first administration of study drug is taken into account in the calculations. Based on these assumptions a total sample size of 132 subjects (121 events) will provide a power of 80%.

A total sample size of 132 subjects will also provide approximately 83% power to detect a 20% reduction in the first key secondary endpoint, using a two-sided chi-squared test with a large sample approximation and a 5% significance level. This assumes incidence rates of 30% and 10% in the placebo and caplacizumab arms, respectively.

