6.2 Secondary Efficacy Endpoints Evaluation

6.2.1 Key secondary endpoints

Key secondary endpoints are defined in Section [3.3.2.1](#).

Confirmatory hypothesis testing will be conducted only for the key secondary endpoints. In order to control the rate of false positive conclusions with a family-wise error rate of 5%, a fixed sequence approach will be applied. The key secondary endpoints are hierarchically ordered. This allows statistical testing for these endpoints at the same nominal significance level of 5% without adjustment, as long as the tests occur in the pre-defined sequential order, and given that all null hypotheses to be tested for endpoints with a higher rank (including the primary endpoint) are rejected. As soon as a test is not statistically significant for a certain endpoint, i.e. as soon as the sequence breaks, no confirmatory testing will be done for remaining endpoints lower in the ranking. Statistical comparison between the two treatment arms for the key secondary endpoints will be done by means of the following planned analyses (in hierarchical order):

1. Proportion of subjects with TTP-related death, a recurrence of TTP, or at least one treatment-emergent major thromboembolic event (e.g., myocardial infarction, cerebrovascular accident, pulmonary embolism or deep venous thrombosis [DVT]) during the overall treatment period (including extensions). Start and end times of the overall treatment period are defined in Section [4.4.1](#). A Cochran-Mantel-Haenszel (CMH) test will be conducted with adjustment for GCS category (stratification factor used in randomization). For both treatment groups, only events that have occurred prior to a switch to open-label caplacizumab will be evaluated for this analysis.

This composite endpoint consists of the following components:

- TTP-related death: adverse event categorized as 'clinically significant TTP event' and documented as 'death due to TTP' and/or adverse events with outcome 'fatal', adjudicated as TTP related (see below).
- TTP recurrence: recurrent thrombocytopenia after initial recovery of platelet count, requiring re-initiation of daily PE. Depending on the timing of recurrence, it is defined as:
 - Exacerbation: recurrence occurring during the first 30-days post-daily PE period
 - Relapse: recurrence occurring after the 30-days post-daily PE period; only relapses within the overall treatment period are taken into account for the key secondary endpoint.

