The following sas code will be used as starting point for the multiple imputation:

```
proc mi data=original n impute=number seed=1 out=imputed minimum=0
round=1;
  by studyid trt01pn trt01p;
  mcmc impute=full;
  var _day1 _day2 _day3 _day4 _day5;
run;

where
ORIGINAL is the input dataset
IMPUTED is the data after imputation
NUMBER is the number of imputation depending on the percentage of
missingness
STUDYID is the study identifier
TRT01P and TRT01PN are respectively the categorical and numeric
versions of the planned treatment groups used for the subjects during
the DB treatment period
_DAYx (x=1 to 5) are the measurements for each subjects from day 1 to
day 5
```

4. Time to first normalization of all three organ damage marker levels, i.e. LDH, cTnI and serum creatinine. Time to first normalization of LDH, cTnI and serum creatinine is defined as: first time of LDH \leq ULN and cTnI \leq ULN and serum creatinine \leq ULN - time of first i.v. loading dose of study drug after randomization + 1 minute. The time to normalization will be represented by number of days with two decimal digits. Subjects in either initial treatment group who have switched to open-label caplacizumab before having reached the endpoint will be censored at time of switch. All on-treatment records during DB treatment period will be used. A stratified Log-rank test will be conducted based on a KM analysis with adjustment for GCS category and for an additional factor defining whether the subject has abnormal values at baseline for LDH only (not for cTnI or for serum creatinine) or not.

In addition to the confirmatory statistical tests, standard summary statistics will be provided for all key secondary endpoints. For the first key secondary endpoint 'proportion of subjects with TTP-related death, a recurrence of TTP, or at least one treatment-emergent major thromboembolic event during the overall treatment period (including extensions)' and for the second key secondary endpoint 'proportion of subjects with a recurrence of TTP in the overall study period' separate summary statistics will be included for the OL Caplacizumab treatment group. For these endpoints also the number of events will be reported.

All analyses will be run on the ITT population.

A detailed list of tables, listings and figures can be found in Section [14.2](#), Section [16.2](#) and Section [15.1](#), respectively.

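### Is the 83% power for the first key secondary endpoint overstated because it has no drop-out allowance and ignores the fixed sequence?

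*SAP*

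**What the plan says.** SAP section 3.2 sizes the trial on the primary endpoint: median time to platelet count response of 7 days on placebo and 4.2 days on caplacizumab, a 45-day window, and a two-sided 5% log-rank test. It says that "an expected drop-out rate of 10% in the first 10 days after first administration of study drug is taken into account", and then: "Based on these assumptions a total sample size of 132 subjects (121 events) will provide a power of 80" per cent.

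A separate paragraph adds that "A total sample size of 132 subjects will also provide approximately 83% power to detect a 20% reduction in the first key secondary endpoint". It names a two-sided chi-squared test at 5% and incidences of 30% on placebo and 10% on caplacizumab. It mentions no drop-out. The protocol synopsis and protocol section 3.1.1 carry the same statement.

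SAP section 6.2.1 makes each key secondary test confirmatory only "given that all null hypotheses to be tested for endpoints with a higher rank (including the primary endpoint) are rejected". For the analysis set of the key secondary endpoints it says: "All analyses will be run on the ITT population".

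The protocol's list of changes for version 3.0 explains the rise from 92 to 132 subjects partly as a step "to account for drop-outs, and to increase the statistical power of the key secondary endpoint analyses".

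**The concern.** Three features invite doubt.

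- The 80% for the primary endpoint includes a drop-out allowance. The 83% beside it has none, and the text does not say so. A reader could conclude that the clinical composite is better powered than the primary endpoint.
- The 83% is the power of one test taken alone. The composite is tested confirmatorily only if the primary endpoint is significant, so the chance of a confirmatory result on it must be lower.
- The reduction is written as 20%, although a move from 30% to 10% is 20 percentage points, or two thirds in relative terms. The 40% quoted for the primary endpoint in the same section is a relative reduction.

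If the true figure were clearly lower, the sponsor's statement that the larger trial serves both drop-out and key secondary power would be weaker than it looks.

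**Working it through.** **1. Reproduce the 83%.** Inputs from SAP 3.2: p1 = 0.30, p2 = 0.10, 132 subjects randomized 1:1 (n = 66 per arm), two-sided 5%. With p̄ = (p1 + p2)/2,

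power = Φ{ [ |p1 − p2| − 1.96·√(2p̄(1 − p̄)/n) ] / √( [p1(1 − p1) + p2(1 − p2)]/n ) }.

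- √(2 × 0.2 × 0.8/66) = 0.0696, and 1.96 × 0.0696 = 0.1365
- √((0.21 + 0.09)/66) = 0.0674
- power = Φ((0.2 − 0.1365)/0.0674) = Φ(0.942) = 82.7%

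The exact power of the Pearson test is 83.8%. The stated figure reproduces with all 132 subjects contributing.

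**2. Reproduce the 80% for the primary endpoint.** Assume exponential times, so the ratio of medians 4.2/7 = 0.6 is the ratio of hazards.

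- Power at 121 events = Φ(½·√121·|ln 0.6| − 1.96) = Φ(5.5 × 0.5108 − 1.96) = Φ(0.850) = 80.2%.
- Event hazards are λ = ln 2/7 = 0.0990 and ln 2/4.2 = 0.1650 per day. A constant drop-out hazard is η = −ln(0.9)/10 = 0.0105 per day.
- P(event by day 45) = λ/(λ + η) × (1 − e^(−45(λ + η))) = 0.897 and 0.940.
- Expected events = 66 × (0.897 + 0.940) = 121.2, which matches the stated 121.
- With no drop-out, 131.2 events are expected and power is 83.3%.

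So the primary figure includes drop-out and the secondary figure has no separate term for it. That observation is correct.

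**3. What drop-out could do to the 83%.** Same formula as step 1, with 10% drop-out:

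| Assumption about drop-outs | Inputs | Power |
|---|---|---|
| 30% and 10% are already incidences in all randomized subjects | 30% v 10%, n = 66 | 82.7% |
| Kept as non-events, half of their events lost | 28.5% v 9.5%, n = 66 | 80.2% |
| Excluded from the analysis | 30% v 10%, n = 59.4 | 78.5% |
| Kept as non-events, all of their events lost | 27% v 9%, n = 66 | 77.4% |

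**4. Which row fits the plan.** The analysis is on all randomized subjects. SAP 6.2.1 excludes early discontinuations only for the third key secondary endpoint (refractory TTP) and gives no such rule for the first. The first counts documented recurrences and adjudicated deaths and thromboembolic events, so a subject with no recorded event is naturally a non-event.

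The phase II data point the same way. Protocol section 1.2.4 reports "exacerbation during treatment of 8% (n = 3) for caplacizumab compared to 28% (n = 11) for placebo". The complete-remission figures there (29 = 80.6%; 18 = 46.2%) imply arms of 36 and 39, which sum to the 75 subjects of the phase II intent-to-treat analysis. 3/36 = 8.3% and 11/39 = 28.2%, so the quoted rates use those denominators and already contain whatever drop-out occurred. This one component alone, at 28% v 8% and n = 66, gives 85.7%.

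**5. The sequence.** The probability that both tests succeed cannot exceed the smaller marginal power, min(0.802, 0.827) = 80.2%. Under a bivariate normal model without drop-out for the composite it is 0.802 × 0.827 = 66% at correlation 0, 71% at 0.5 and 75% at 0.8. The correlation is an assumption; the documents give none.

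**The case for a change.** The best case for a change is that the text never says how an early drop-out with no recorded event is counted in the first key secondary endpoint. SAP section 4.2.2 leaves missing values out of percentage denominators and 4.2.4 imputes nothing by default, so exclusion is not ruled out in so many words. The phase II exacerbation rates cover only one component and do not prove that 30% and 10% are net of drop-out. On the lost-information rows, the composite has 77.4% to 80.2% against 80.2% for the primary endpoint, so the apparent advantage disappears. One or two sentences would remove the doubt at no cost.

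Part of this stands. There is no explicit drop-out term, and the text does not say whether the two rates are net of drop-out. The rest is weaker.

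- Exclusion fits poorly with an analysis of all randomized subjects in which presence of an event is what is recorded. Losing every drop-out's events is an extreme case, since a TTP-related death is itself an event.
- The comparison with 80.2% mixes two drop-out models: a constant hazard to day 45 for the primary endpoint and a one-off 10% loss for the composite. If drop-out stops after day 10, the primary calculation gives 123.8 events and 81.1%.
- Uncertainty in the assumed rates is larger than the drop-out effect. SAP section 1 cites a post-hoc phase II result of 43.2% v 11.4% for major thromboembolic events or death. At 66 per arm that would give 98.9% power, and at 59.4 per arm 98.1%. This is illustrative only, because the composite here also includes recurrence.
- The plan sets a power target, at least 80%, only for the primary endpoint. It sets none that the composite could miss.

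**Conclusion.** No change is needed. The 83% is right for its stated inputs (82.7%), and it stands as it is if 30% and 10% are incidences in all randomized subjects, which is the reading that best fits the analysis population and the event-based endpoint. Otherwise the loss is about 3 to 5 points, and only under assumptions about exclusions or lost events that the plan does not make.

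That the figure is stand-alone power is evident from the single test, significance level, sample size and pair of rates given with it. Quoting it that way in a fixed sequence is common practice. The gate is set out in full in SAP 6.2.1, the protocol synopsis and protocol 3.6.4.2. The upper limit of about 80% for passing both tests restates the primary endpoint's power, and anything lower depends on a correlation that the documents do not give. The wording of the reduction is a small looseness that the next sentence resolves by giving both rates.

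The sample size follows from the primary endpoint, and control of type I error is unaffected. Saying that 83% is stand-alone power, that the rates are assumed for all randomized subjects, and that the difference is in percentage points would be an optional courtesy to the reader. It would alter no number, rule or conclusion.

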3.3 Study endpoints

This section mainly describes the endpoints defined for adult subjects.

The objective for the pediatric substudy is to report the efficacy, safety, PK and PD properties and immunogenicity of caplacizumab in pediatric subjects experiencing an acute episode of acquired TTP. In this sense the endpoints are partly similar to those of the adult population but the feasibility of any specific analysis will, to a large extent, depend upon the amount of available data (i.e., the number of pediatric patients included). In case the total number of patients in the pediatric group is smaller than 3, only listings but no summary tables will be created. Results for the pediatric substudy will be reported separately.

3.3.1 Primary endpoint

The primary endpoint of the study is: time to platelet count response. Platelet count response is defined as initial platelet count $\geq 150 \times 10^9/L$ with subsequent stop of daily PE within 5 days.

3.3.2 Secondary endpoints

3.3.2.1 Key secondary endpoints

The key secondary endpoints are hierarchically ordered as listed below:

1. Proportion of subjects with TTP-related death, a recurrence of TTP, or at least one treatment-emergent major thromboembolic event during the study drug treatment period (including extensions).
2. Proportion of subjects with a recurrence of TTP in the overall study period (including the 4-week follow-up [FU] period).
3. Proportion of subjects with refractory TTP, defined as absence of platelet count doubling after 4 days of standard treatment, and LDH $>$ upper limit of normal range (ULN).

CONFIDENTIAL

4. Time to normalization of all 3 of the following organ damage marker levels: LDH, cTnI, serum creatinine.

3.3.2.2 Other secondary endpoints

- Proportion of subjects with recurrences of TTP as well as the number of such events during study drug treatment (including extensions) and after study drug treatment.
- Proportion of subjects with treatment-emergent clinically significant TTP-related events, as well as the number of such events in the overall study period (including 4-week FU period). Clinically significant TTP-related events are defined as one of the following events:
 - Neurological
 - Defined as presence of coma, stupor, seizures, disorientation/confusion, hemiparesis/-plegia, focal deficit, agitation, and dysarthria (For more details see CSP Section 3.4.3.3)
 - Cardiovascular
 - Elevated cardiac troponins (value and local upper limit of reference range)
 - Acute myocardial infarction (ECG finding)
 - Conduction abnormality (ECG finding)
 - Repolarization abnormality (ECG finding)
 - Heart failure (severity)
 - Other (to be specified)
 - Exacerbation
 - On study-drug relapse
 - Post-study drug relapse
 - Death due to TTP
 - Other (to be specified)
- Area under the curve (AUC) of platelet count until Day 5, truncated at $150 \times 10^9/L$ if platelet count is $150 \times 10^9/L$ or above.
- Mortality rate during 4 analysis periods: double-blind (DB) treatment daily PE period, overall treatment period, follow-up (FU) period and overall study period.
- Organ damage markers: Time to $LDH \leq 1 \times ULN$
- Organ damage markers: Time to $cTnI \leq 1 \times ULN$
- Organ damage markers: Time to serum creatinine $\leq 1 \times ULN$
- Proportion of subjects with increases in organ damage markers (cTnI and serum creatinine) above $1 \times ULN$ in 4 analysis periods: DB treatment daily PE period, overall treatment period, FU period and overall study period.

- AUC of cTnI above 1 x ULN during DB treatment daily PE period and during overall treatment period.
- Proportion of subjects with neurological symptoms based on neurological assessment on Day 1, 2, 3, 4, 5 and on Weeks 1 and 5 of the 30-day post-daily PE treatment period, and the first and the final FU visit.
- Change from baseline in Standardized mini mental state examination (SMMSE) total score on Days 1, 2, 3, 4, 5 and on Weeks 1 and 5 of the 30-day post-daily PE treatment period, and on the first and the final FU visit. Where:
 - SMMSE: 30-point validated test used to examine the cognitive mental status of a subject. The SMMSE measures various domains of cognitive functions including orientation to time and place; registration; concentration; short-term memory; naming familiar items; repeating a common expression; and the ability to read and follow written instructions. The resulting total score is corrected for degree of schooling and age.
- Proportion of subjects with evidence of cardiac ischemia and/or arrhythmia/conduction abnormalities on Days 1, 2, 3, and 4, and Weeks 1 and 5 of 30-day post-daily PE treatment period, and the first and final FU visit.
- Proportion of subjects who have a platelet count $\geq 150 \times 10^9/L$ on Day 1, 2, 3, 4, 5 and Day 10 and at end of study drug treatment (i.e., last weekly visit during the treatment period).
- Proportion of subjects with refractory TTP, defined according to Scully et al. (2016) as lack of sustained platelet count increment or platelet counts $< 50 \times 10^9/L$ and persistently raised LDH ($> 1.5 \times \text{ULN}$) despite 5 plasma exchanges and steroid treatment.
- Time to stop of daily PE.
- Bleeding events.
- (S)AEs, laboratory data, vital signs, ECG and physical examinations.
- PE parameters: number of days and total volume in 2 time periods, i.e. DB treatment daily PE period and overall treatment period.
- Number of days in ICU and in hospital in 4 time periods: DB treatment daily PE period, overall treatment period, FU period (of 4 weeks after stop of study treatment) and overall study period.
- PD parameters: vWF: Ag concentration, FVIII: C activity and RICO activity.
- PK parameters: study drug concentrations.
- Immunogenicity: ADA, mADA, NAb, and alternative NAb.

Note: The components of composite key secondary endpoints (both proportion of subjects and number of events) will also be analyzed separately as 'other secondary endpoint'.

